2. STATEMENT OF COMPLIANCE

The trial will be carried out in accordance with Good Clinical Practice (GCP) as required by the following:

- United States (US) Code of Federal Regulations (CFR) applicable to clinical studies (45 CFR Part 46, 21 CFR Part 50, 21 CFR Part 56, and 21 CFR Part 312) [SEP]
- ICH E6 [SEP]

All key personnel (all individuals responsible for the design and conduct of this trial) have [SEP] completed Human Subjects Protection Training. [SEP]

I agree to ensure that all staff members involved in the conduct of this study are informed about their obligations in meeting the above commitments.

Project Director:

Print/Type Name

Signed:

Signature

Date: _____

Site Principal Investigator:

Print/Type Name

Signed:

Signature

Date: _____

3. Protocol Synopsis
Title of study: A Phase 2, Proof-of-Concept, Double-Blind-Randomized, Placebo-Controlled Adaptive Design Trial of Nicotinamide in MCI due to AD and Mild AD Dementia
Background: Nicotinamide, the amide of nicotinic acid (vitamin B3/niacin), is an oral therapy with a wealth of clinical data in a variety of therapeutic areas, including preliminary data supporting its safety in Alzheimer’s disease (AD). Preclinical work in a mouse model that develops both plaques and tangles supports the hypothesis that nicotinamide can act as a histone deacetylase (HDAC) inhibitor to reduce phosphorylation of tau. ^{1,2} In this mouse model of AD, treatment with nicotinamide reduced p-tau, increased microtubule stability and rescued cognitive function.
Developmental phase: Phase 2
Research objectives: 1: Determine if daily treatment with high dose nicotinamide can reduce levels of phosphorylated tau in individuals with mild AD dementia or MCI due to AD. 2: Assess the safety and tolerability of high dose nicotinamide treatment in individuals with mild AD dementia or MCI due to AD.
Study design: Group sequential design, incorporating a futility analysis with a go/no-go decision conditional on CSF biomarker outcomes at 48-weeks.
Duration of study: Screening period: Up to 60 days Treatment period: 48-weeks
Sample size: 48
Study population: Patients age 50 or older who meet criteria for MCI due to AD or Mild AD dementia (Mini-Mental State Exam [MMSE] ≥ 20) not otherwise excluded.
Dose and administration: Nicotinamide is an oral tablet that will be administered at 1500 mg (two 750 mg tablets) BID.
Primary outcome: Change in CSF p-tau ₂₃₁
Secondary outcomes: 1. Change in CSF p-tau ₁₈₁ 2. Change in CSF total tau 3. Change in CSF A β ₄₂ 4. Change in CSF A β ₄₀ 5. Change in ADAS-cog13 6. Change in ADCS-ADL 7. Change in CDR-SB
Safety parameters: Adverse events, symptom checklist, vital signs, physical, neurological examination and laboratory tests.
Go/No-go decision: An additional 48-weeks treatment and follow-up period is planned, contingent upon a “go” decision based on the primary outcome (CSF p-tau ₂₃₁) or one planned secondary outcome (CSF p-tau ₁₈₁)
Statistical methods: The study will implement a seamless phase 2a-2b sequential design with a go/no-go futility analysis based upon change in CSF biomarkers after 48-weeks. The primary outcome for the trial is change in p-tau ₂₃₁ . Inference for the initial go/no-go decision will be based upon the difference in within-subject change in p-tau ₂₃₁ or p-tau ₁₈₁ over 48-weeks between treatment and control.

7. BACKGROUND

Treatments capable of slowing the progression of Alzheimer's disease (AD) are desperately needed. Though a variety of promising candidates are in development,³ there are no approved drugs able to slow AD.⁴ Anti-amyloid therapies dominate the clinical pipeline but if shown to be effective will have great cost, may require routine infusions, and may be associated with substantial risk for serious adverse events.⁵ Some experts argue that there is an over-emphasis on amyloid beta (A β)-targeting therapies in clinical development and most agree that there is a need to explore alternate hypotheses and therapeutic targets.⁶ Safe and effective oral therapies that are capable of slowing the disease process represent a major therapeutic goal in AD research.

Neurofibrillary tangles represent the pathological hallmark of AD that is most strongly correlated with cognitive decline.^{7,8} Neurofibrillary tangles are composed of hyperphosphorylated tau, a microtubule associated protein critical to neuronal viability. Elevated levels of tau phosphorylated at threonine 231 (p-tau₂₃₁) in the cerebrospinal fluid (CSF) can be used to distinguish AD from normal controls and other neurodegenerative conditions,^{9,10} are correlated with neurofibrillary tangle burden at autopsy,¹¹ and are predictive of progression to dementia among patients with mild cognitive impairment (MCI).¹² Therefore, this biomarker substrate of AD pathology may be a meaningful target for candidate disease-modifying therapies.

Nicotinamide, or niacinamide, is a key component of nicotinamide adenine dinucleotide (NAD), a co-enzyme involved in many cellular oxidation-reduction reactions and vital for cellular respiration. Nicotinamide also acts as a free radical scavenger, and modulates both immune cell function and apoptosis. In addition to these crucial roles, high doses of nicotinamide function to inhibit the class 3 histone deacetylases (HDACs), or sirtuins. Sirtuins are a unique class of NAD(+)-dependent deacetylases required for diverse biological processes including autophagy, transcription, and apoptosis. Sirtuins function to remove acetyl groups from their substrate proteins, and in doing so regulate cellular pathways. In this process the acetyl group is passed from the substrate to an NAD molecule. The presence of nicotinamide within the cell competes with free pools of NAD, however, and thereby prevents this process from occurring. It has been found that regulating protein acetylation can be broadly protective and as such HDAC inhibitors are being pursued as potential treatments for numerous neurodegenerative diseases.¹³ Four months of nicotinamide treatment (200 mg/kg/day) in triple transgenic AD mice (3xTg), which develop both amyloid plaques and neurofibrillary tangles,¹⁴ selectively decreased the accumulation of p-tau₂₃₁ by 60% in AD-vulnerable brain regions and significantly ameliorated cognitive decline, without affecting levels of A β .¹ Treatment also increased acetylated alpha-tubulin and microtubule-associated protein 2c levels, enhancing microtubule stabilization.¹ Importantly, laboratories at the National Institute on Aging have replicated the effects of nicotinamide on tau phosphorylation in 3xTg mice. This group also found beneficial effects on A β pathology as well as improved brain bioenergetics with preserved functionality of mitochondria and the autophagy system.² Thus, there is a strong pre-clinical rationale for testing the hypothesis that nicotinamide can act as an HDAC inhibitor to reduce p-tau in AD.

Notably, trials in other neurologic conditions support the hypothesis that nicotinamide can act as an HDAC inhibitor. In Friedreich's ataxia, high dose nicotinamide (3.5-6g/day) resulted in a dose-response upregulation of expression of frataxin mRNA and overall increases in frataxin protein levels,¹⁵ presumably due to HDAC inhibition, as protein changes were accompanied by decreased heterochromatin modifications in the *FXN* gene.^{15,16} Nicotinamide has also been shown to be beneficial/protective in animal models of stroke,¹⁷ traumatic brain injury,¹⁸⁻²⁰ Parkinson's disease,^{21,22} and Huntington's disease,²³ emphasizing the rationale that nicotinamide may be therapeutic in CNS diseases, and that it modulates specific pathways implicated in AD pathogenesis.

Large human clinical trials demonstrate the safety of high dose nicotinamide. For example, in a study of more than 550 participants with a first-degree family history of Type I diabetes, no differences between nicotinamide and placebo were observed for any adverse event.²⁴ The daily dose in this study was mean 1.2 g/m² up to a maximum of 3g/day for five years. Similarly, in a phase 3 study of twice daily 500 mg

nicotinamide to prevent recurrent non-melanoma skin cancer (n=386), no differences were observed in adverse event profiles between those randomized to nicotinamide and those randomized to placebo. Treatment with nicotinamide also reduced the occurrence of new basal cell and squamous-cell carcinomas by 20% and 30%, respectively.²⁵

We previously performed a single-site safety trial in humans with mild-to-moderate AD (Schreiber et al., *in preparation*). Participants age 50 or older with a diagnosis of probable AD and Mini-Mental State Exam (MMSE) scores 13-26, inclusive, were enrolled. Exclusion criteria were a diagnosis of non-AD dementia, unstable psychiatric disease or medical illness, history of alcoholism, drug abuse, liver disease or peptic ulcer disease, and Hachinski Ischemic Score >4 or evidence of stroke on magnetic resonance imaging (MRI) or computed tomography scan. Participants were required to be on stable medications for at least 30 days, including FDA-approved therapies for AD. Participants were not permitted to take supplements containing nicotinamide. Participants were required to have a study partner who could accompany them to visits and ensure compliance with the study treatment.

We randomized 31 participants to receive nicotinamide (Endur-amide [Niacinamide, vitamin B3] 1500 mg orally bid, Endurance Products Company, Tigard, OR), or a matching placebo for 24 weeks. The randomization was 1:1, with no stratifications. The dose of nicotinamide approximated that used in preclinical studies and was comparable to other human trials.^{24, 25} Adverse events were recorded at weeks 6, 12, 18 and 24. Safety laboratories (tests of liver function [LFTs], serum electrolytes and complete blood count [CBC]) were assessed at week 4. Vital signs, physical and neurological examinations were assessed at baseline and week 24. Pill counts assessed compliance. In addition to safety assessments, we completed the 11-item cognitive subscale of the Alzheimer's Disease Assessment Scale (ADAS-cog11), Clinician's Interview-Based Impression of Change Plus Caregiver Input (CIBIC-Plus), Alzheimer's Disease Cooperative Study-Activities of Daily Living Scale (ADCS-ADL), and the Clinical Dementia Rating Scale (CDR) at baseline and weeks 6, 12, 18, and 24.

Participants in the active and placebo groups were mean age 79.7±6.9 and 79.0±8.4, respectively, and had mean MMSE scores of 22.1±3.17 and 21.3±3.6. Fifty-six percent of subjects in the treatment group were male, compared to 80% in the placebo group. Twenty-eight participants (90%) completed the study. Treatment compliance was 72% in both groups.

No adverse events resulted in participant withdrawal from the study. We observed no adverse effects of nicotinamide on serum electrolytes, CBC or LFTs. The most frequent adverse event was visual hallucination or delusions (n=4 nicotinamide, n=4 placebo). There was no difference between the groups on clinical outcome measures. The conclusion of this Phase 2a study is that nicotinamide can be safely administered at a dose of 3000 mg/day in patients with mild-to-moderate AD.

In summary, nicotinamide is a promising intervention for neurodegenerative disease that may specifically target neurofibrillary pathology in AD. Nicotinamide is safe at high doses and over long durations of treatment in humans. No study has tested the hypothesis that nicotinamide can inhibit HDAC to reduce phosphorylation of tau in people with AD.

8. STUDY OBJECTIVES

8.1. Primary Objectives

Objective 1: Determine if daily treatment with high dose nicotinamide reduces levels of phosphorylated tau (p-tau₂₃₁) in individuals with mild AD dementia or MCI due to AD.

Objective 2: Assess the safety and tolerability of high dose nicotinamide treatment in individuals with mild AD dementia or MCI due to AD.

8.2. Secondary Objectives

Secondary Objective 1: Determine if daily treatment with high dose nicotinamide can affect CSF levels of amyloid beta ($A\beta_{42}$), phosphorylated tau ($p\text{-tau}_{181}$), total tau ($t\text{-tau}$), or the ratio of total tau/ $A\beta$ in individuals with mild AD dementia or MCI due to AD.

Secondary Objective 2: Determine if daily treatment with high dose nicotinamide reduces the rate cognitive decline in individuals with mild AD dementia or MCI due to AD.

Secondary Objective 3: Determine if daily treatment with high dose nicotinamide reduces the rate of functional decline in individuals with mild AD dementia or MCI due to AD.

8.3. Exploratory Objectives

Exploratory Objective 1: Determine if daily treatment with high dose nicotinamide reduces the rate of brain volume atrophy in individuals with mild AD dementia or MCI due to AD.

Exploratory Objective 2: Determine the effect size of 48-weeks change in phosphorylated tau in individuals with mild AD dementia or MCI due to AD.

9. INVESTIGATIONAL PLAN

9.1. Overall Study Design and Plan

This is a Phase 2a group sequential design, incorporating a futility analysis with a go/no-go decision conditional on CSF biomarker outcomes at 48-weeks. With a go-decision, follow-up will be extended to 96-weeks in a Phase 2b trial, with dual co-primary outcomes of the 13-item cognitive subscale of the Alzheimer's Disease Assessment Scale (ADAS-cog13) and the Alzheimer's Disease Cooperative Study-Activities of Daily Living Scale (ADCS-ADL). The purpose of the Phase 2b trial is to provide preliminary measures of efficacy to facilitate the design of a larger registration trial.

The initial trial primary outcome is CSF $p\text{-tau}_{231}$. We will randomize 48 participants to 1500 mg BID nicotinamide or matched placebo at a 1:1 ratio. Additional CSF analyses ($p\text{-tau}_{181}$, total tau, $A\beta_{40}$, $A\beta_{42}$) will be performed as secondary outcomes in the proposed Phase 2a trial. A portion of the CSF sample will be stored for future biomarker analyses. Clinical measures will be collected every 24-weeks throughout the study and will be considered secondary outcome measures in the initial trial. Cognitive and functional outcomes will include ADAS-cog13, ADCS-ADL, and CDR sum of boxes (CDR-SB). Additionally, we will examine change in brain volume (whole brain volume, ventricular volume, hippocampal volume, and cortical thickness) as exploratory secondary outcome measures.

9.2. Study Procedures

9.2.1. Visit schedule (see Appendix 1).

- Screening period: Three visits will determine eligibility. An initial clinical visit will include completion of informed consent, MMSE, Wechsler Logical Memory II, FCSRT, CDR-SB, GDS, physical and neurological examinations including vital signs, medical history and collection of concomitant medications, and assessment of inclusion and exclusion criteria. This visit will also include a blood draw for apolipoprotein E (APOE) genotyping, safety labs, urinalysis (UA), and electrocardiogram (EKG). Assuming that participants have had clinical neuroimaging within the previous 12-months to exclude the possibility of space-occupying lesion, the second visit will include lumbar puncture (LP) and fasting blood draw for future biomarker research. A third visit will include MRI for screening and baseline volumetric assessment. For participants lacking clinical neuroimaging in the previous 12-months, the order of LP and MRI visits may be reversed. If needed, redraw of blood can be performed to check platelet level and coagulation parameters within 30 days prior to LP.

- Active period: Eligible participants will have a brief physical and neurological exam including vital signs, collection of adverse events and concomitant medications, cognitive testing (MMSE and ADAS-cog), be administered the C-SSRS, GDS, and ADCS-ADL-MCI, will receive study medication, and undergo safety labs (blood and urine) at the baseline exam. Telephone follow-up at 2, 4, and 36-weeks will assess safety. At 12-weeks, an in-person visit will include a brief physical and neurological exam including vital signs, collection of adverse events and concomitant medications, blood collection for drug levels, fasting blood collection for future biomarkers, EKG, assessment of treatment compliance and administration of study medication. At 24 and 48-weeks, participants will undergo blood safety labs, urinalysis (UA), blood collection for drug levels, blood collection for future biomarkers, and EKG. Participants will complete the MMSE, ADAS-cog13, ADCS-ADL-MCI, CDR-SB, GDS, C-SSRS physical and neurological examinations, including vital signs, collection of adverse events and concomitant medications. MRI, LP, and fasting blood collection for future biomarkers will be performed at 48-weeks.
- End of study: At 48-weeks, participants will complete all study assessments. Participants will be provided additional study drug (6-months supply) for the period of time for go/no-go analysis.
- Early termination: In the event of early termination due participant withdrawal of consent or removal by the investigator from the trial, the 48-weeks/early termination visit should be completed in all possible cases, if the participant has been randomized to therapy or placebo. No new investigational product will be administered.
- Unscheduled visits: If needed, unscheduled visits can be performed at the discretion of the Site Principal Investigator. Unscheduled visits should include collection of adverse events, concomitant medications, brief neurological and physical examination, and clinical blood laboratories, if indicated.
- Go/no-go: At the completion of the go/no-go analyses, participants will complete an additional visit to assess safety and collect study medication (no-go) or to be enrolled in the 48-weeks extension study (go). In the event of a “go” decision, trial duration will be extended to 96-weeks. Participants will remain blinded to randomization and group assignment will be unchanged. A safety visit will be performed at 74-weeks. The end of study visit will be performed at 96-weeks, and will include the co-primary outcome measures of the ADAS-cog13 and the ADCS-ADL-MCI, as well as the CDR-SB, neurological and physical exams, blood laboratories, assessment of adverse events, MRI, and lumbar puncture for CSF protein analysis.

9.2.2. Safety assessments. Participants will undergo brief physical and neurological examinations, laboratory testing, and EKG at all follow-up visits (12, 24, and 48-weeks /early termination). Adverse events will be assessed by the study site clinician. Adverse events include signs or symptoms that may or may not be related to study medication, abnormalities detected during physical examination, or clinically significant laboratory abnormalities. The Columbia Suicidality Severity Rating Scale (C-SSRS) will be performed at the baseline, 24-week, and 48-week visits. Adverse events will be graded as mild, moderate, or severe according to section 13.1.1, and recorded on case report forms. Regular safety reports will be prepared by the ADCS and submitted to an independent Data and Safety Monitoring Board (see section 13.3.3).

9.2.3. Laboratory evaluations. Routine safety laboratory studies will include CBC, chemistries and urinalysis at screening, and lipids and liver function tests at follow-up visits (24 and 48-weeks/early termination).

9.2.4. Treatment compliance. At each follow-up visit (12, 24, and 48-weeks/early termination), participants will bring their study medication diaries and their study medications for the purpose of standard pill counts. The over-the-counter availability of nicotinamide presents the challenge that participants could purchase and take the study intervention. We will assess blood levels of N1-

Methylnicotinamide, 2-Pyridone (a nicotinamide metabolite) and blood levels of NAD at the 12-, 24- and 48-week visits.^{26, 27} For these visits, study medication should be held until in the clinic, to optimize measures of compliance. Eighty percent compliance is expected. If there is an insufficient level of drug compliance, the site must consult with the Project Directors and Medical Monitor regarding timing and procedures. It is possible that subjects will be discontinued early from the study due to insufficient compliance.

9.2.5. Lumbar puncture. Within 30 days prior to lumbar puncture, participants' coagulation panel and platelet count will be measured and verified within normal limits. Lumbar puncture (LP) will be performed under fasting conditions (minimum 8-hour fast). Only water (and any medications that can be taken without food) is permitted until LP is complete. LP will be performed as close to 08:00AM as possible. Participants will be in a seated position for the LP, if possible. LP will be performed using a small caliber atraumatic needle (e.g. 22 or 24 gauge Sprotte needle.) LPs will be permitted to be performed under guided fluoroscopy if CSF is unable to be obtained by bedside LP. CSF will be collected by gravity flow or aspiration method, at the discretion of the site clinician. All syringes, tubing, collection tubes, and transfer tubes will be polypropylene. A total of 18mL of CSF will be collected. The first 2mL fraction of CSF will be sent to local lab for measurement of cell counts and differential, glucose, and protein. The next 16mL of CSF will be immediately placed on ice during transfer and aliquot procedures, frozen at -80°C, then shipped overnight on dry ice on the day of collection to ADCS Biomarker Core. Time of collection, verification of fasting status, type and gauge of needle, method of collection, and total volume of CSF collected will be recorded.

9.2.6. Data Management. Data will be collected on Case Report Forms (CRFs), identifying subjects only by study ID number. Electronic data will be entered into the ADCS Electronic Data Capture (EDC) System.

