14.2. Analysis of the primary outcome

The primary analysis of phase 2a will focus on the change in p-tau₂₃₁. The primary analysis will be based on the Intention-to-Treat population, defined as all participants who were randomized to study drug or treatment. We will model the change in p-tau₂₃₁, using an analysis of covariance model (ANCOVA). That is, 48-week p-tau₂₃₁ will be regressed upon baseline p-tau₂₃₁ and an indicator for treatment vs. placebo. The Huber-White robust variance estimator will be used to estimate the variance of the estimated difference in the mean change in p-tau₂₃₁ comparing treatment to placebo. Along with the estimated difference in mean change in p-tau₂₃₁, a Wald-based 95% confidence interval and corresponding p-value will be computed and presented.

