5.5.2 Early Termination

Early termination from the study includes participants who leave the study and/or discontinue treatment prior to completing the week 48 visit. Proportions of participants who prematurely discontinued the study prior to the week 48 visit will be compared between the study arms.

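### Poor compliance can end study participation, not only treatment, and the plan does not say how a removed participant's CSF enters the 48-week primary analysis

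*Protocol*

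**What the plan says.** **Removal.** Protocol 9.2.4 states an expectation ("Eighty percent compliance is expected") and a process ("If there is an insufficient level of drug compliance, the site must consult with the Project Directors and Medical Monitor regarding timing and procedures"). It then adds: "It is possible that subjects will be discontinued early from the study due to insufficient compliance". No level of compliance is defined as insufficient. Compliance is checked at weeks 12, 24 and 48 or early termination.

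**After removal.** Under early termination, which covers removal by the investigator, Protocol 9.2.1 asks that "the 48-weeks/early termination visit should be completed in all possible cases, if the participant has been randomized to therapy or placebo". In the Appendix 1 schedule that visit shares a column with week 48, and the column includes a lumbar puncture. No later follow-up to week 48 is described.

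**Analysis.** Protocol 14.2 says: "The primary analysis will be based on the Intention-to-Treat population, defined as all participants who were randomized to study drug or treatment". SAP 4.1 also defines this population without a compliance condition. Protocol 14.2 and SAP 5.1 regress 48-week p-tau231 on baseline and treatment. Protocol 14.5 and SAP 5.1 and 5.8 rule out imputation in the primary analysis.

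**Disposition.** SAP 5.5.2 says: "Early termination from the study includes participants who leave the study and/or discontinue treatment prior to completing the week 48 visit".

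**Pilot (Protocol section 7).** "Treatment compliance was 72% in both groups", over 24 weeks. Also, "Twenty-eight participants (90%) completed the study".

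**The concern.** Compliance is observed after randomisation, so removing people for it is not random with respect to outcome. An intention-to-treat analysis needs the week-48 outcome from everyone randomised, including those who took few tablets. The plan allows such participants to leave and does not ask for their CSF at week 48. It also does not say what to do with the CSF collected when they leave.

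There are two possible outcomes. If early-termination CSF is not counted, the participant drops out of a comparison still labelled intention-to-treat. If it is counted, a shorter period of disease and treatment is analysed as 48 weeks. Either way, Objective 1 is answered for something other than the week-48 effect in all randomised participants. The trial is small: 48 planned with 10% loss leaves 48 × 0.9 = 43.2, about 43 evaluable.

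The planned per-protocol comparison would not reveal the problem. SAP 4.1 defines that set as participants who completed to week 48 with a lumbar puncture. If early-termination CSF is excluded, this is almost the same set as the intention-to-treat participants with data.

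**Working it through.** **1. The plan's own figure.** Inputs from Protocol 14.4 and SAP 1.3: N = 48, 1:1 allocation, 10% loss, SD 1.5, difference 1.26 pg/ml, power about 80%. Alpha is not stated there; two-sided 0.05 is inferred from the 95% interval.

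- n per arm = 24 × 0.9 = 21.6
- SE = 1.5 × √(2/21.6) = 0.456
- Power = Φ(1.26/0.456 − 1.96) = 78.8%

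The stated power reproduces. The 10% makes no separate allowance for compliance removals.

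**2. Removed participants without usable 48-week CSF.** The documents give no removal rate, so a share c is assumed on top of the 10% loss. The top value, 28%, is 100 − 72: the pilot figure read as the share of participants who complied, with all the others removed. It is an extreme, not an estimate.

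- n per arm = 21.6 × (1 − c)
- Effect in all randomised = 1.26 × [(1 − c) + c × f], where f is the fraction of the effect that non-compliers get
- Overstatement = 1/[(1 − c) + c × f] − 1

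This assumes that those who remain show the full 1.26 and that prognosis without drug is the same in compliers and non-compliers.

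| c | n per arm | Power at 1.26 | Overstatement, f = 0.5 | Overstatement, f = 0 |
|---|---|---|---|---|
| 5% | 20.5 | 76.8% | 3% | 5% |
| 10% | 19.4 | 74.5% | 5% | 11% |
| 20% | 17.3 | 69.5% | 11% | 25% |
| 28% | 15.6 | 64.9% | 16% | 39% |

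At c = 28% the SE rises from 0.456 to 1.5 × √(2/15.55) = 0.538, an interval 18% wider.

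**3. Early-termination CSF counted as the 48-week value.** Assume that the planned 5.1 pg/ml rise and the 1.26 effect both accrue linearly over the 48 weeks, and that removal comes at week 24, one of the compliance checks.

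- A placebo sample then shows 5.1 × 24/48 = 2.55 pg/ml less rise than at week 48, about twice the 1.26 target.
- The nicotinamide rise over 48 weeks is 5.1 − 1.26 = 3.84, so half is 1.92.
- Estimated difference = 5.1 × (1 − cP/2) − 3.84 × (1 − cN/2), where cP and cN are the shares sampled early on placebo and nicotinamide.
- 10% in both arms: 4.845 − 3.648 = 1.197, a 5% dilution.
- 10% on nicotinamide only: 5.1 − 3.648 = 1.452, an overstatement of 0.192.
- 10% on placebo only: 4.845 − 3.84 = 1.005, an understatement of 0.255.

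The direction therefore depends on which arm loses more people.

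**4. Is the choice between steps 2 and 3 settled anywhere?** SAP 5.2 names early termination beside week 48 for ECG data. SAP 5.3.3 names the last available measurement in a fallback for the clinical scales. SAP 5.1 and Protocol 14.2 mention only week 48 for p-tau231. The question is left open.

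**The case against.** The strongest reply is that the plan already protects the outcome. The early-termination visit expressly covers removal by the investigator and includes a lumbar puncture. The population is all randomised, and even the per-protocol set has no compliance criterion. Removal is only possible, not automatic, and consultation comes first. SAP 5.8 plans multiple imputation as a sensitivity analysis, Protocol 14.5 adds a pattern-mixture analysis, Protocol 14.6.1 adds a compliance-adjusted analysis, and SAP 5.5.1 reports withdrawals with reasons by arm.

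Much of this stands, and it rules out several stronger readings:

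- **Removal forfeits the CSF outcome.** Not so: a sample is requested, and what is unsettled is its timing and use.
- **The intention-to-treat result becomes a compliers' result.** Non-compliers who are not removed stay in, and removed ones may contribute CSF. The estimate can move in that direction; the documents do not show that it arrives there.
- **The pilot shows that many would be removed.** The 72% may be a mean pill count or a share of participants. It was the same in both arms, and it sits beside completion by 28 of 31 and no withdrawal for adverse events. The 80% is an expectation, not a removal limit. The pilot makes compliance below 80% plausible, nothing more.
- **Side effects would make removal differ by arm.** The nausea, vomiting and diarrhoea in Protocol 11.2 come from ten patients at individual doses of 2-8 g/day and are introduced as a matter of doses above 3 g/day. This trial uses 3 g/day, and the same section reports no adverse-event differences in two large trials.

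The reply does not supply a request for week-48 CSF after removal or a rule for early-termination CSF. The pattern-mixture analysis is not carried into the SAP. SAP 5.5.2 excludes nobody from analysis, but it hides the distinction a reader needs.

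**Conclusion.** The point holds as a gap in follow-up and in the definition of the outcome, and it should be closed. A removed participant is either missing from the primary comparison or represented by a sample from the wrong time.

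The size cannot be computed from the documents, because there is no cut-off and no distribution of individual compliance. Under assumed further removals of 5-28% without usable CSF, power falls from about 79% to 77-65%. The all-randomised effect is then overstated by 3-16% if non-compliers get half of it, or 5-39% if they get none. These figures treat removals as additional to the 10% loss and as yielding no usable CSF. Any overlap with that loss, or a week-48 sample obtained and used, reduces them. If early samples are instead counted as 48-week values, the error can go either way.

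**What to change.** **Protocol 9.2.4.** Keep the consultation step, and state that insufficient compliance alone does not end study participation. Whatever is decided about study drug, the participant stays in scheduled follow-up with the week-48 lumbar puncture and clinical measures, unless consent is withdrawn. This leaves every study-drug decision where it is.

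**SAP 5.5.2.** Report *stopped study drug* and *left the study* as separate categories by arm, with removals for non-compliance shown.

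**SAP 5.1 and 5.8.** State that early-termination CSF is not a 48-week value in the primary model. Use it in a sensitivity analysis that accounts for time since baseline.

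**Cost.** One protocol sentence and a few lines of SAP text; the visits and lumbar punctures are already in the schedule. The intention-to-treat estimate will include some low-exposure participants, as it should, but retention does not always raise power. With 10% non-compliers at half effect, power is 74.6% if they are kept (21.6 per arm, effect 1.197) against 74.5% if removed. At no effect it is 70.0% (effect 1.134) against 74.5%. The gain is an answer for the randomised population.

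SAP 3.1 reports 47 participants already randomised. The protocol change helps only those still in follow-up; for anyone already removed, only the SAP changes apply.
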